Clinical Trial Protocol

Document Number:		c21847264-03
EudraCT No.	2018-001177-24	
BI Trial No.	1199-0340	
BI Investigational Medicinal Product(s)	Nintedanib	
Title	A Phase I trial to investigate the effect of nintedanib on the pharmacokinetics of a combination of ethinylestradiol and levonorgestrel in female patients with Systemic Sclerosis associated Interstitial Lung Disease (SSc-ILD)	
Lay Title	A study to test whether nintedanib influences the components of birth-control pills in women with Systemic Sclerosis associated Interstitial Lung Disease (SSc-ILD)	
Clinical Phase	I	
Trial Clinical Monitor	Phone: Fax: E-mail:	
Coordinating Investigator	Phone: Fax: E-mail:	
Status	Final Protocol (Revised Protocol (based on global amendment 2))	
Version and Date	Version: 3.0	Date: 29 Apr 2019
Page 1 of 108		
Proprietary confidential information. © 2019 Boehringer Ingelheim International GmbH or one or more of its affiliated companies. All rights reserved. This document may not - in full or in part - be passed on, reproduced, published or otherwise used without prior written permission.		

CLINICAL TRIAL PROTOCOL SYNOPSIS

Company name	Boehringer Ingelheim
Protocol date	06 July 2018
Revision date	29 Apr 2019
BI trial number	1199-0340
Title of trial	A Phase I trial to investigate the effect of nintedanib on the pharmacokinetics of a combination of ethinylestradiol and levonorgestrel in female patients with Systemic Sclerosis associated Interstitial Lung Disease (SSc-ILD)
Coordinating Investigator	
Trial site(s)	Multi-centre trial conducted in approximately 6 countries
Clinical phase	I
Trial rationale	Nintedanib is a potential human teratogen, which is intended for use in fertile women. In accordance to the European Medicines Agency (EMA) guideline on the investigation of drug interactions, this trial will investigate the in vivo effect of nintedanib on contraceptive steroids.
Trial objective(s)	To investigate the effect of multiple oral doses of nintedanib on the single dose kinetics of a combination of ethinylestradiol and levonorgestrel (Microgynon [®])
Trial endpoints	Primary endpoints: 
• AUC_{0-tz} and C_{max} for ethinylestradiol and levonorgestrel Secondary endpoints: 
• AUC_{0-∞} for ethinylestradiol and levonorgestrel
Trial design	Open-label, two-period, fixed sequence
Total number of patients enrolled	Approximately 24 patients
Total number of patients on treatment	14 patients who have completed the trial and are evaluable for both treatment periods
Diagnosis	Patients with Systemic Sclerosis associated Interstitial Lung Disease (SSc-ILD)
Main inclusion criteria	Women ≥ 18 years, permanently sterilised or postmenopausal or using a highly effective non-hormonal method of birth control (i.e. intra-uterine device (IUD), bilateral tubal ligation) in combination with a barrier methods; Systemic Sclerosis associated Interstitial Lung Disease (SSc-ILD), fulfilling the 2013 ACR / EULAR classification criteria for SSc; extent of fibrotic lung disease ≥10% on high resolution computed tomography (HRCT); Forced Vital Capacity (FVC) ≥40% of predicted; carbon monoxide diffusion capacity of the lungs (DLCO) 30% to 89% predicted (corrected for Hb).

Main exclusion criteria	Abnormal liver (alanine transaminase (ALT), aspartate transaminase (AST) and bilirubin > 1.5x upper level of normal (ULN)) and renal (creatinine clearance < 30 mL/min) parameters; significant pulmonary hypertension; cardiovascular disease within 6 months of Visit 1 (hypertension (\geq 160/100 mmHg); myocardial infarction, unstable angina pectoris); high bleeding risk; history of major thrombotic event within 12 months of Visit 1, concomitant use of P-glycoprotein (P-gp)-, cytochrome P450 3A4 (CYP3A4) inhibitors or inducers medications, certain immunosuppressive agents.
Reference product	Microgynon [®] tablet
dose	One tablet containing 30 microgram ethinylestradiol (EE) and 150 microgram levonorgestrel (LE) per tablet in each trial period
method and route of administration	Oral with 240 mL of water
Test product	Nintedanib soft gelatine capsule (containing 150 mg or 100 mg nintedanib)
dose	150 mg b.i.d (300 mg daily) with possibility to interrupt and/ or reduce to 100 mg b.i.d (200 mg daily) to manage adverse events (AE), if required
method and route of administration	Oral with food and 240 mL of water
Duration of treatment	
Period 1:
 
 1 tablet of Microgynon[®] will be administered on the first pharmacokinetics (PK) profile day, after a standardised breakfast, at least 3 days before the first administration of nintedanib. 
Period 2:
 
 Nintedanib (150 mg b.i.d.) will be administered at Day 1. Nintedanib treatment will be continued for at least 14 days to approximately 28 days in this trial, depending on scheduling of the PK day, or nintedanib dose interruptions or dose reduction. After continuous intake of a stable dose of nintedanib for at least 10 consecutive days, the PK day will be planned. On the PK-profile day, 1 tablet of Microgynon[®] will be given immediately after the morning dose of nintedanib, after a standardised breakfast. The evening dose of nintedanib will be administered approximately 12 hours after the morning dose of nintedanib. The PK-profile day should be followed by continuous intake of nintedanib for at least 2 further days.
Statistical methods	Relative exposure of ethinylestradiol and levonorgestrel will be estimated based on the ratios (test to reference treatment) of the geometric means (gMeans) of the primary and secondary endpoints. Additionally, their 2-sided 90% confidence intervals (CIs) will be

	
provided. The statistical model will be an analysis of variance (ANOVA) on the logarithmic scale, including effects for 'subject' and 'treatment'. CIs will be calculated based on the residual error from ANOVA.
 
Descriptive statistics will be calculated for all endpoints.

--	--

FLOW CHART

Trial Periods	Screening Visit *	Period 1 *			Period 2 **					End of Treat. #	Follow Up ##	End of Study #
		2 *	3	4	5	5A	6 ***	7	8			
Visit	1	2 *	3	4	5	5A	6 ***	7	8	EOT	FU	EOS
Day	-14	-3	-2	-1	1	10	11	12	13	14	EOT+7	14 or EOT+7
Time window (±Days)	±7	V2 +1	V2 +2			V6 -1	+14	+1	V6 +2	V6 +3	+2	+2
Informed consent ¹	x											
Demographics	x											
Medical history (SSc related ² and other baseline conditions)	x											
Physical examination and vital signs	x	x					x			x	x	
In-/Exclusion criteria	x	x										
HRCT ³	x											
Spirometry ⁴	x									x		
DLCO ⁴	x											
Echocardiogram ⁵	x											
mRSS assessment	x											
Digital ulcer assessment	x											
Questionnaires ⁶ : SGRQ, SHAQ, SCTC GIT, patient and physician global VAS	x											
Laboratory tests	x	x			x ⁷		x			x	x	
Pregnancy test ¹¹	x				x					x	x	
12-lead ECG	x	x								x	x	
PK diary: instruction, handout and review					x	x	x	x	x			
PK sampling pre-dose for nintedanib (trough) ⁸							x	x	x			
Dispense nintedanib + continuous (b.i.d.) intake of nintedanib					x	x	x ⁹	x	x			
PK sampling pre-dose Microgynon [®]		x					x					
Standardized meal before Microgynon [®] intake		x					x					
Administration of Microgynon [®]		x					x ⁹					
PK Sampling, after Microgynon [®] intake ¹⁰		x	x	x			x	x	x			
All AEs/SAEs/ AESIs	x	x	x	x	x	x	x	x	x	x	x	
Compliance check		x			x	x	x	x	x	x		
Concomitant therapy	x	x	x	x	x	x	x	x	x	x	x	
Completion of patient participation												x

Footnotes:

- * Screening Visit 1 may take place within Day -21 to Day -7, or earlier, depending on required washout of restricted medications prior to the 1st Microgynon[®] intake at Visit 2 (see Section [4.2.2.1](#))
Period 1/Visit 2: The 1st Microgynon[®] intake and start of pharmacokinetics (PK) profiling during Period 1 must take place at least 3 days (72 hours) prior to first intake of nintedanib (Visit 5/Day 1); results of Screening Visit 1 examinations need to be awaited prior to proceeding with Period 1. In case of clinically significant electrocardiogram (ECG) or laboratory abnormalities at Visit 1, these examinations have to be repeated at an unscheduled Visit prior to Visit 2 in order to assess if the patient is still eligible and safe to continue the trial.
- ** Period 2 starts with Visit 5/Day 1 when the patient begins with the daily intake of nintedanib. During Period 2, the nintedanib intake compliance will be checked with a Telephone Call one day prior to plan PK Visit 6.
- *** Visit 6 will take place at Day 11, but may be scheduled until Day 25 (a visit window of +14 days is allowed) and will only be conducted when the patient has had at least 10 days of continuous nintedanib intake (b.i.d) at stable dose. If the patient is not able to continuously take nintedanib (150 mg b.i.d.) for at least 10 days* then Visit 6 (and the 2nd Microgynon[®] administration and PK assessments) must be postponed until at least 10 days of continuous nintedanib on stable dose was taken by the patient (* e.g. in case of a temporary interruption or nintedanib dose reduction, additional bottles of nintedanib may have to be dispensed at Visit 6, or at an Unscheduled Visit and the V5-V6 visit window can be prolonged accordingly). The next Visits must be scheduled accordingly.
- # For patients that fully complete the trial and continue in the roll-on trial 1199-0225 (SENSCIS-ON), the End of Treatment (EOT) Visit and End of Study (EOS) Visit can be done simultaneously and must be done at the earliest 3 days after last intake of Microgynon[®]. For patients that prematurely and permanently discontinue the Microgynon[®] and/or nintedanib treatment in Periods 1 or 2, or patients that will not continue in the roll-on trial 1199-0225, the EOT Visit must be done as soon as possible after stop of treatment, and a Follow-Up (FU) Visit must be scheduled 7 days (± 2 days window) after last nintedanib intake.
- ## The FU Visit must be done 7 days ± 2 days window) after last nintedanib intake, but only in the following cases: (a) If trial medication will be discontinued permanently due to adverse events, or (b) if the patient will not continue in the roll-over Trial 1199.225. No FU Visit will be done if the patient is directly being rolled over into Trial 1199.225. For the patients (a) and (b) the FU Visit will be done simultaneously with the EOS Visit.
- ¹ Before or at the latest at Visit 1. Informed consent (IC) needs to be signed before any procedure related to the trial is performed. All adverse events (AEs) and concomitant therapies (CTs) from the day of signing informed consent have to be recorded.
- ² SSc related Medical History includes onset date of Raynaud symptom, onset of first non-Raynaud symptom, SSc subtypes, and check list of symptoms present at screening, e.g. digital ulcers, gastrointestinal and urinary symptoms, cardiovascular and pulmonary symptoms.
- ³ SSc related Interstitial Lung Disease pattern must be confirmed by high resolution computed tomography (HRCT) of the lung performed within 12 months of Visit 1. If the patient does not have a HRCT within 12 months of Visit 1, but meet all the other inclusion and no exclusion criteria, the HRCT scan can be performed for the purpose of participation in the trial, if accepted by local regulations (except for patients in Germany). The extent of fibrotic disease in the lung must be $\geq 10\%$ on HRCT, assessed by local review.
- ⁴ Forced vital capacity (FVC) $\geq 40\%$ of predicted normal at Visit 1. Lung function measurements at Visit 1 and at EOT must be done at the approx. the same time ± 90 min. At screening visit 1, spirometry should be done prior to carbon monoxide diffusion capacity of the lungs (DLCO) and the patient should rest in between.
- ⁵ Echocardiography will at least be performed in patients with a history of pulmonary hypertension at Screening (time window: Visit 1 to Visit 2).
- ⁶ Self-reported outcome questionnaires must always be done by the patients in a quiet place prior to any other visit procedure. Order of questionnaires: 1. SGRQ, 2. SHAQ, 3. SCTC GIT, 4. Patient's global VAS (see Appendix [10.3](#)). The SCTC GIT will only be done in countries if the locally required language version is available.
- ⁷ Laboratory safety test at Visit 5, Day 1 should be done prior to intake of nintedanib in order to get baseline laboratory values without Microgynon[®] (past the Microgynon[®] residual effect period (REP) of 3 days) or nintedanib related effects.
- ⁸ PK sampling before intake of nintedanib in Period 2 (Visits 6-8) will be done as described in the PK overview on the following pages, which also contains detailed information about other assessments and timing of intake of meals and water.
- ⁹ In Period 2/Visit 6 Nintedanib will be administered first directly followed by Microgynon[®] and both have to be intaken within 1 minute on the PK day.

- ¹⁰ Detailed information about timing and assessments during PK days in Periods 1 and 2 can be found in the overviews on the following pages. PK sampling after Microgynon[®] intake will be done at approximate timepoints t = +30 min to +12 h (9 times), at t = +24 h and t = +48 h. During PK day in Periods 1 and 2, at t = 20 h and 4 h, administration of 240 mL of water.
- ¹¹ Pregnancy testing will only be done in women of childbearing potential: β -HCG will be performed at Visit 1 only. Urine dipstick pregnancy tests will be performed at Visits 5 and EOT and FU visit if applicable. If urine test is not acceptable to local authorities, a blood test can be also done by local laboratory if needed.

Detailed overview and order of assessments on PK days in Period 1:

Period 1, Visits 2-4				
Day	Relative. time to Microgynon® intake [h:min]	Approx. Clock Time* [h:min]	Assessment/comment	PK blood for EE and LE
Visit 2, Day -3	Pre-dose		Physical examination	
	Pre-dose		Review in/exclusion criteria	
	Pre-dose		Vital signs	
	Pre-dose		12-lead ECG	
	Pre-dose		Safety Laboratory tests (preferably after ECG)	
	Pre-dose		Adverse events	
	Pre-dose		Concomitant therapy	
	Pre-dose		Compliance check	
	-00:35	07:25		x
	-00:30	07:30	Breakfast (standardized)**	
	00:00	08:00	Microgynon® intake*	
	00:30	08:30		x
	01:00	09:00		x
	01:30	09:30		x
	02:00	10:00	240 mL water	x
	03:00	11:00		x
	04:00	12:00	240 mL water + lunch	x
	06:00	14:00		x
	08:00	16:00		x
	10:00	18:00	Snack	
	11:55	19:55	AE	x
Visit 3, Day -2	23:55	07:55	AE, CT, Compliance	x
Visit 4, Day -1	47:55	07:55	AE, CT, Compliance	x

Note:* The exact clock time of intake of Microgynon® and blood sampling must be recorded during the PK profiling days in this Period; ** Standardized, i.e. the same breakfast in Period 1 and Period 2 for an individual patient.

Detailed overview and order of assessments on PK Visit days in Period 2:

Period 2, Visits 6 - 8					
Day	Relative time to Microgynon intake [h:min]	Approx. Clock Time* [h:min]	Assessment/comment	PK blood for EE and LE	PK blood for nintedanib
Visit 6, Day 11	Pre-dose		Physical examination		
	Pre-dose		Vital signs		
	Pre-dose		Safety Laboratory tests		
	Pre-dose		Adverse events		
	Pre-dose		Concomitant therapy		
	Pre-dose		Compliance check		
	-00:35	07:25		x	x
	-00:30	07:30	Breakfast (standardized)**		
	00:00	08:00	Microgynon® intake immediately after Nintedanib intake* (both to be taken within 1 minute)		
	00:30	08:30		x	
	01:00	09:00		x	
	01:30	09:30		x	
	02:00	10:00	240 mL water	x	
	03:00	11:00		x	
	04:00	12:00	240 mL water + lunch	x	
	06:00	14:00		x	
	08:00	16:00		x	
	10:00	18:00	Snack		
	11:55	19:55	AE	x	
	12:00	20:00	Nintedanib intake*		
Visit 7, Day 12	23:55	07:55	AE, CT, Compliance	x	x
	24:00	08:00	Nintedanib intake*		
Visit 8, Day 13	47:55	07:55	AE, CT, Compliance	x	x
	48:00	08:00	Nintedanib intake*		

Note:* The exact clock time of intake of trial medication must be recorded in the 3 days prior to and during the PK profiling days in Period 2. And also the exact clock time of all blood samples during the PK profiling days in Period 2 must be recorded; ** Standardized, i.e. the same breakfast in Period 1 and Period 2 for an individual patient.

TABLE OF CONTENTS

TITLE PAGE	1
CLINICAL TRIAL PROTOCOL SYNOPSIS	2
FLOW CHART	5
TABLE OF CONTENTS	10
ABBREVIATIONS	14
1. INTRODUCTION.....	19
1.1 MEDICAL BACKGROUND.....	19
1.2 DRUG PROFILE	20
1.2.1 Nintedanib.....	20
1.2.2 Ethinylestradiol.....	24
1.2.3 Levonorgestrel.....	25
1.3 RATIONALE FOR PERFORMING THE TRIAL	26
1.4 BENEFIT - RISK ASSESSMENT.....	26
1.4.1 Nintedanib.....	26
1.4.2 Microgynon.....	28
1.4.3 Potential interaction between nintedanib and Microgynon.....	29
1.4.4 Drug induced liver injury.....	29
2. TRIAL OBJECTIVES AND ENDPOINTS.....	30
2.1 MAIN OBJECTIVES, PRIMARY AND SECONDARY ENDPOINTS.....	30

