Nintedanib does not induce CYP enzymes *in vitro* nor in rats *in vivo* ([U09-1731](#), [U04-2195](#)). Therefore, the likelihood of nintedanib causing a relevant pharmacokinetic drug-drug interaction on oral contraceptives by induction of their metabolism that would lead to a loss of the pharmacodynamic action of these drugs is considered to be very low. Due to teratogenic potential of nintedanib the EMA DDI guidance from 2012 nevertheless requires to perform a clinical study to investigate the potential effect of nintedanib on the PK of oral contraceptives.

Residual Effect Period

The Residual Effect Period (REP) of nintedanib is 7 days

The Residual Effect Period (REP) of Microgynon[®] is 3 days.

The REP is the period after the last dose with measurable drug levels and/or pharmacodynamic effects still likely to be present.

Data from non-clinical and toxicology studies

In rats, embryo-foetal lethality and teratogenic effects were observed at exposure levels below human exposure at the Maximum Recommended Human Dose (MRHD) of 150 mg twice daily. Effects on the development of the axial skeleton and on the development of the great arteries were also noted at subtherapeutic exposure levels.

In rabbits, embryo-foetal lethality and teratogenic effects were observed at an exposure approximately 3 times higher than at the MRHD but equivocal effects on the embryo-foetal development of the axial skeleton and the heart were noted already at an exposure below that at the MRHD of 150 mg twice daily.

In a pre- and postnatal development study in rats, effects on pre- and post-natal development were seen at an exposure below the MRHD.

A study of male fertility and early embryonic development up to implantation in rats did not reveal effects on the male reproductive tract and male fertility.

In rats, small amounts of radiolabelled nintedanib and/or its metabolites were excreted into the milk ($\leq 0.5\%$ of the administered dose).

Data from clinical studies

The clinical efficacy of nintedanib has been studied in over 1400 patients with IPF in one Phase II dose finding trial (TOMORROW) including four different doses of nintedanib, and

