3.3.4.3 Withdrawal of consent to trial participation

Patients may withdraw their consent to trial participation at any time without the need to justify the decision.

If a patient wants to withdraw consent, the investigator should be involved in the discussion and explanation to the patient.

When the patient prematurely discontinues the trial medication a follow-up Visit will be done 7 days after last intake of nintedanib, please see Section [3.3.4.1](#) above and the [Flow Chart](#).

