5.2.10.2 Adverse event collection and reporting

5.2.10.2.1 AE Collection

The investigator shall maintain and keep detailed records of all AEs in the patient files. The following must be collected and documented on the appropriate eCRF(s) by the investigator:

- From signing the informed consent onwards until the individual patient's End of Study (EOS):
 - All AEs (serious and non-serious) and all AESIs.
- After the individual patient's End of Study:
 - The investigator does not need to actively monitor the patient for new AEs but should only report any occurrence of cancer and related SAEs and related AESIs of which the investigator may become aware by any means of communication, e.g. phone call. Those AEs should however not be reported in the eCRF but via SAE form.
 - For an individual patient that completes the study and will participate in the roll-on Trial 1199-0225 and continues nintedanib treatment in that trial, the collection of adverse events for this trial will stop once the trial was completed for this respective patient. Any ongoing AE or new AE that occurs after End of Study (EOS) Visit must be reported in the roll-on trial 1199-0225.
 - For an individual patient that discontinues the trial early in Period 1, after intake of Microgynon[®], the collection of AE will stop after the end of the REP of Microgynon[®] (i.e. 3 days).
 - For an individual patient that discontinues the trial early in Period 2 or for any patient that decides not to participate in the roll-on Trial 1199-0225, nintedanib treatment will stop and the collection of AE will stop after the end of the REP for nintedanib (i.e. 7 days) at the Follow-Up (FU) Visit.

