6.2.3 Trial completion

Before trial completion the patient and investigator will assess whether the patient will

- a) Stop nintedanib treatment in this trial and continue nintedanib therapy in the roll-on Trial 1199-0225, or
- b) Permanently stop the nintedanib treatment and perform a Follow-Up Visit 7 days after permanent discontinuation of nintedanib.

For patients who complete this trial (a) and continue in the roll-on Trial 1199-0225, the investigations, as documented in the [Flow Chart](#) EOT Visit and EOS Visit, will be performed simultaneously at the earliest 3 days after last intake of Microgynon[®]. These last assessments performed at the EOT/EOS Visit will be considered the baseline data for the roll-on trial 1199-0225, in which the patients will enroll the same day or shortly after.

For patients who permanently discontinue the nintedanib treatment (prematurely or not) (b) and/or who will not continue in the roll-on Trial 1199-0225, the investigations as documented in the Flow Chart EOT Visit will be done immediately after stop of nintedanib, or at least 3 days after Microgynon[®] intake (if applicable) and the FU Visit and EOS Visit will be performed simultaneously 7 days after last intake of nintedanib.

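### Flow Chart footnotes # and ## allow the FU/EOS visit on day 5 after the last nintedanib dose, so routine AE recording can stop up to 2 days before the 7-day residual effect period ends

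*Protocol*

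**What the plan says.** **Visit window.** Footnote ## to the Flow Chart states "The FU Visit must be done 7 days ± 2 days window) after last nintedanib intake". Footnote # agrees: the FU "Visit must be scheduled 7 days (± 2 days window) after last nintedanib intake". In the Flow Chart row labelled "Time window (±Days", the FU and EOS cells each read +2, with FU placed at EOT+7. The text sections give a nominal day without a window. Section 3.3.4.3 says the follow-up "Visit will be done 7 days after last intake of nintedanib", and Section 6.2.3 says "the FU Visit and EOS Visit will be performed simultaneously 7 days after last intake of nintedanib".

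**Link to EOS.** For patients who stop permanently because of adverse events or do not continue into 1199-0225, footnote ## adds that "the FU Visit will be done simultaneously with the EOS Visit".

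**AE collection.** Section 1.2.1 states: "The Residual Effect Period (REP) of nintedanib is 7 days". Under Section 5.2.10.2.1 all AEs are collected until the patient's EOS. After that there is no active monitoring. Only cancers, related SAEs and related AESIs that come to the investigator's attention are reported, by SAE form and not in the eCRF. For patients who stop in Period 2 or do not roll over, the same section says "the collection of AE will stop after the end of the REP for nintedanib (i.e. 7 days) at the Follow-Up (FU) Visit".

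**Analysis.** Protocol Section 7.3.4 counts AEs after EOS as on-treatment for nintedanib if they fall within 7 days of the last dose. SAP Section 4 says that AEs starting after EOS will not be in the database. SAP Table 6.1: 1 ends the last nintedanib phase on the day after last contact for patients who do not roll over.

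**The concern.** The protocol gives sites two different windows for the same visit, and one of them conflicts with the AE collection rule. Section 5.2.10.2.1 expects collection to reach the end of the REP and to stop at the FU visit. Both can be true only if FU takes place on day 7 or later. The minus side of the footnotes allows day 5 or 6, and the visit then also closes the patient's participation.

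What is at stake is the completeness of the descriptive on-treatment AE tables for patients who have an FU visit, including those who stopped nintedanib because of an adverse event. The events that could be lost are new-onset AEs late in the REP, mainly non-serious AEs and SAEs or AESIs judged unrelated. The PK endpoints are not involved.

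**Working it through.** There is no planned figure to reproduce. The check is day arithmetic, counting the day of the last nintedanib dose as day 0.

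**Inputs**
- Footnotes # and ##: 7 ± 2 days after last nintedanib intake.
- Time-window row: +2 for FU and EOS, FU at EOT+7. Other cells in the row carry their own signs (±7, V6 -1, +14), so +2 is not shorthand for ±2 despite the row label.
- REP: 7 days (Section 1.2.1).
- Last intake is the evening before, or at, the EOT visit (Section 4.1.4). For patients who stop early, EOT follows the stop of treatment (footnote #). EOT is therefore never before last intake.
- Terminal half-life: 7 to 19 h (Section 1.2.1).

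**Window under the footnotes**
- Earliest 7 − 2 = day 5, latest 7 + 2 = day 9: 5 possible days, of which days 5 and 6 precede the end of the REP.

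**Window under the row**
- Earliest EOT+7, latest EOT+9: 3 possible days. Since EOT is not before last intake, none is earlier than day 7.

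**Part of the REP without routine eCRF recording** = max(0, 7 − visit day)

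| FU/EOS on day | Uncovered days | Share of REP |
|---|---|---|
| 5 | 2 | 2/7 = 29% |
| 6 | 1 | 1/7 = 14% |
| 7 to 9 | 0 | 0% |

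**Does anything later recover these days?** No. Section 7.3.4 would count such events as on-treatment, but SAP Section 4 confirms they will not be in the database. The SAP's nintedanib phase follows the last contact date rather than last dose plus 7 days, and no contact after FU/EOS is scheduled for these patients.

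**Drug remaining at day 5 (120 h)**, assuming mono-exponential decline, fraction = 0.5^(120 / half-life)
- Half-life 19 h: 120/19 = 6.3 half-lives, 0.5^6.3 = 1.3%.
- Half-life 7 h: 120/7 = 17.1 half-lives, less than 0.001%.

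**The case against.** The strongest reply is that the intent is clear and the harm slight. Section 5.2.10.2.1 ties the end of collection to the end of the REP, and Section 7.3.4 keeps events within 7 days of the last dose on-treatment. A site that stopped on day 5 would be departing from the first of these. That shows the intent but does not close the gap: Section 5.2.10.2.1 itself names the FU visit as the stopping point, and the SAP rules out later entries.

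Several narrower objections carry some weight:

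- **Sections 3.3.4.3 and 6.2.3.** They state a nominal 7 days with no late window either, and Section 6.1 refers to the Flow Chart for windows. They are weak evidence against the footnotes. The conflict with the row and with Section 5.2.10.2.1 does not depend on them.
- **Reference day.** The row counts from EOT and the footnotes from last intake. If EOT fell 3 days after the last dose, the row would give days 10 to 12 and a corrected footnote days 7 to 9. This is a separate mismatch. It does not affect the point here, because both then fall on day 7 or later.
- **Amendment 1.** Its list of minor corrections includes the FU/EOS time window, which suggests that the row is the revised version. It does not say what changed, so nothing here rests on it.
- **Impact.** Cancers, related SAEs and related AESIs remain reportable, AEs persisting at EOS are followed up (Section 5.2.10.2.3), and the safety analysis is descriptive. All of this stands and keeps the importance modest.

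**Conclusion.** The point holds. An FU/EOS visit that complies with the footnotes can end routine eCRF AE recording up to 2 days before the protocol's own 7-day REP ends: 29% of its days at worst, 14% with a day-6 visit and none from day 7.

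These are shares of days, not of events. The documents do not say how many of the approximately 24 enrolled patients will have an FU visit, so the number affected cannot be estimated. With 1.3% or less of the drug remaining at 120 h, few drug-related events are likely to be missed. The shortfall is measured against the REP that the protocol chose. Patients who roll over directly have no FU visit and are unaffected.

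The conclusion assumes that a site uses the early side of the window and has no later contact with the patient that is recorded in the eCRF. It is a real inconsistency of modest importance, worth correcting because the correction is so simple.

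**What to change.** In footnotes # and ##, replace ± 2 days with +2 days, keeping 7 days after last nintedanib intake as the reference. FU/EOS then falls on days 7 to 9, the early side disappears as in the Flow Chart row, and the uncovered part of the REP drops from at most 2 days to 0.

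The cost is two footnote edits and no extra visit. Scheduling becomes tighter, with 3 possible days instead of 5. The same edit is a convenient moment to state one reference day (last intake or EOT) in both the row and the footnotes, although closing the gap does not require it.
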